4.1.2 Post Treatment Evaluation

Participants will be scheduled to have a clinical examination at 1 week and within 4 - 6 weeks and at 12 – 16 weeks post therapy. In the event that a suspicious lesion is observed, participants will be scheduled for a biopsy at the discretion of the treating physician, at 4-6 weeks post treatment. In addition, a scheduled pathological evaluation will be conducted by taking a 3-mm punch biopsy from the treated tumor site during the clinical visit at 12-16 weeks post therapy.

Tumor response will be determined at 24 months post treatment. The treating physician will examine the clinical response and a photograph of the treatment site will be taken with paper ruler, to determine the reduction in the lesion size, according to RECIST v1.1. A biopsy may be taken, if clinically indicated. The biopsies will be processed following the standard of care pathology. A clinical pathologist will examine the processed tissue section and determine the pathological response.

Participants who have partial or no-response will be offered standard therapy, at the discretion of the treating physician.

We hypothesize that non-responders or partial responders in the PDT arm are likely to be participants whose tumor does not retain HPPH. For this subset of participants that are treated with PDT at RPCI, an additional biopsy (50 mg tissue mass) will be taken at the time of excision of the recurrent tumor to evaluate cellular mechanisms that contribute to tumor retention of HPPH. The biopsy sample is immediately dropped into a sterile 15-ml screw-cap tissue culture tube containing 5 ml of serum-free RPMI medium. A set of such tubes are prepared prior to surgery and can be stored at 4°C for up to a month until use. A research nurse (or other personnel in the operating room, OR) will label the sample tube with an identifier code pertaining to the case, but without inclusion of any PHI. The tube containing the biopsy sample will be placed either into a refrigerator or bucket of ice until pick-up by a member of the investigating laboratories (Drs. [name] or [name], as detailed below). The OR personnel will inform the research associate in the laboratories of either [name] or [name] via telephone or text message. The

associate will pick-up the sample tube at the entrance to the OR and immediately carry it to the laboratory of [name], or [name].

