4.3 MANAGEMENT OF THE NECK AND SALVAGE SURGERY

The management of the neck will be according to standard of care, at the discretion of the treating surgeon. If the participant, based on the pathology of the neck dissection or primary oral cancer resection, has perineural invasion, extracapsular spread, or requires additional therapies including radiation or chemotherapy, they will be dropped from the study and replaced with another participant.

Participants will receive standard curative therapy 6 weeks after failing to respond to PDT with HPPH. All the participants who will have disease progression, local recurrence, or partial or no response (PR, NR) following the PDT with HPPH will be considered treatment failures. The determination will be performed during the study visits, and based on clinical exam and pathology, if clinical exam is unclear.

The surgeon will provide a surgical plan for every patient, including those randomized to PDT. If the patient requires salvage surgery post-PDT, the surgeon will compare the salvage surgery specimen diameter to the diameter of the spot size used for PDT. This data will be used to demonstrate whether PDT affects the surgical plan.

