9 EFFICACY EVALUATIONS

9.1 OBJECTIVE TUMOR RESPONSE

Pathological tumor response will be evaluated by taking a 3-mm punch biopsy from the PDT treated or surgical area at 12-16 weeks after PDT or surgery. The participants from the PDT and surgery arms will be followed clinically up to 2 years. At the end of the follow up time, the treating physician will examine the clinical response and a photograph of the treatment site will be taken with paper ruler, to determine the reduction in the lesion size, according to RECIST v1.1. The study coordinator or nurse will take the photos. The treating physician will determine the lesion size with a caliper if photos can't be taken.

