9.2 TARGET LESIONS

All identifiable lesions will be recorded with digital photography and clinical examination. The objective tumor response will be determined according to the following criteria per Recist v1.1:

- **Complete Response (CR):** Disappearance of all target lesions. Any lymph nodes must have a reduction in short axis to < 10 mm.

- **Partial Response (PR):** At least a 30% decrease in the sum of diameters of target lesions, taking as reference the baseline sum diameters. A biopsy will be taken from the suspected lesions for histological confirmation of squamous cell carcinoma.
- **Progressive Disease (PD):** At least a 20% increase in the sum of diameters of target lesions, taking as references the smallest sum on study (this includes the baseline sum if that is the smallest on study). In addition to the relative increase of 20%, the sum must also demonstrate an absolute increase of at least 5 mm. The appearance of one or more new lesions is also considered progression.
- **Stable Disease (SD):** Neither sufficient shrinkage to qualify for PR nor sufficient increase to qualify for PD, taking as reference the smallest sum diameters while on study, the response will be listed with stable disease. In this case, a biopsy will be taken from the suspected lesion for histological confirmation.

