9.3 EVALUATION OF RESPONSE

Time point response assessments will be performed 12 - 16 weeks and 24 months after PDT. To determine time point response, refer to **Table 4** below.

Table 4 Time Point Response Criteria (+/- non-target disease)

Target Lesions	Non-Target Lesions	New Lesions	Overall Response
CR	CR	No	CR
CR	Non-CR/Non-PD	No	PR
CR	Not evaluated	No	PR
PR	Non-PD or not all evaluated	No	PR
SD	Non-PD or not all evaluated	No	SD
Not all evaluated	Non-PD	No	NE
PD	Any	Yes or No	PD
Any	PD	Yes or No	PD
Any	Any	Yes	PD

The best overall response is the best response recorded from the start of study treatment until follow-up is completed or the participant goes off study (the end of treatment taking into account any requirement for confirmation).

- **Symptomatic Deterioration:** Participants with global deterioration of health status requiring study withdrawal without objective evidence of disease progression at that time, and not related to study treatment or other medical conditions should be reported as progressive disease due to “symptomatic deterioration.” Every effort should be made to document objective progression even after discontinuation of treatment due to symptomatic deterioration. Symptomatic deterioration that may lead to study withdrawal includes, but is not limited to, symptoms such as:
 - Weight loss > 10% of body weight.

- Worsening of disease-related symptoms (e.g., worsening dyspnea, increasing pain/increasing requirement for narcotic analgesics).
- Decline in performance status of > 1 level on ECOG scale.

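### The treatment-failure rule is written for PDT only and is not tied to the 24-month primary response, so how a failure before month 24 is scored is undefined and may differ by arm

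*Combined protocol and SAP*

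**What the plan says.** Section 4.3 (Management of the Neck and Salvage Surgery) states that disease progression, "local recurrence, or partial or no response (PR, NR) following the PDT with HPPH will be considered treatment failures". It adds: "The determination will be performed during the study visits, and based on clinical exam and pathology, if clinical exam is unclear". Nothing equivalent is written for a recurrence after surgery.

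The primary endpoint is defined elsewhere:

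- Section 4.1.2: "Tumor response will be determined at 24 months post treatment".
- Section 9.1: "The participants from the PDT and surgery arms will be followed clinically up to 2 years", and then "At the end of the follow up time, the treating physician will examine the clinical response".
- Section 9.2, with no distinction by arm: "The appearance of one or more new lesions is also considered progression".
- Section 9.3: "Time point response assessments will be performed 12 - 16 weeks and 24 months after PDT". It also defines a best overall response and does not say whether that is the primary endpoint.
- Section 12.3 sends scoring to 9.2 and 9.3, not to 4.3, and makes every randomized participant evaluable.

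On leaving the study, 7.3 and 7.4 treat progression as a reason to stop and require end-of-study evaluations at withdrawal. Section 12.2 rules out imputation.

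On planning, 12.1 assumes 85% complete response in both arms. It cites 82% in the earlier HPPH study and a local recurrence rate of up to 20% after initial surgery. Section 2 frames the hypothesis as cure at the time of initial treatment.

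**The concern.** A participant whose disease recurs at month 8, is re-resected and is clear at month 24 has two defensible scores. One is failure, because the assigned treatment did not hold. The other is complete response, because the month-24 examination shows no lesion. The plan does not choose. For PDT, 4.3 supplies a failure label but does not link it to the endpoint. For surgery there is no label. A participant who leaves at progression has a withdrawal evaluation, but nothing says that it stands as the 24-month value.

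The case will arise. The protocol expects recurrence of up to 20% after surgery, says in 1.2 that recurrences usually go to further surgery, and reports that all PDT failures in its earlier study were salvaged. Response is judged by the treating physician in an open-label trial, so the choice should not wait until results are known.

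**Working it through.** **Inputs.** From 12.2: n = 57 per arm, margin 0.20, Farrington-Manning score test, nominal level 0.05 (side not stated for this test), true rates 85% and 85%, power about 80%. The share s of failures credited as response after salvage is not in the documents; 25% and 50% are assumptions.

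**Statistic.** z = (p_PDT − p_surgery + 0.20) / s0, where s0 = √{[a(1−a) + b(1−b)]/57}, and a (PDT) and b (surgery) are the estimates restricted to b − a = 0.20.

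**The plan's own power.** At 0.85 in both arms, a = 0.708 and b = 0.908, so s0 = 0.0714. The unrestricted standard error is √(2 × 0.85 × 0.15/57) = 0.0669.

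- One-sided 0.025: Φ[(0.20 − 1.96 × 0.0714)/0.0669] = Φ(0.898) = 81.5%. Exact binomial enumeration gives 83.2%.
- One-sided 0.05: 89.1%, exact 89.8%.

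The stated 80% therefore matches one-sided 0.025, which is used below, with 0.05 in brackets.

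**Scored rates under each reading.** If a share s of failures is credited, a true rate p is scored as p + (1 − p)s. For surgery at 0.85: 0.85 + 0.15 × 0.25 = 0.8875 and 0.85 + 0.15 × 0.50 = 0.925. For PDT at 0.65: 0.65 + 0.35 × 0.25 = 0.7375 and 0.65 + 0.35 × 0.50 = 0.825. Probability of declaring non-inferiority, by exact enumeration:

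| Reading | True PDT / surgery | s = 0 | s = 25% | s = 50% |
|---|---|---|---|---|
| Credit to surgery only (power) | 85% / 85% | 83% (90%) | 70% (80%) | 51% (64%) |
| Credit to surgery only (false non-inferiority) | 65% / 85% | 2.6% (5.2%) | 0.7% (1.7%) | 0.1% (0.4%) |
| Credit in both arms (false non-inferiority) | 65% / 85% | 2.6% (5.2%) | 10% (17%) | 34% (46%) |
| Credit to PDT only (false non-inferiority) | 65% / 85% | 2.6% (5.2%) | 21% (32%) | 70% (80%) |

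Equal credit is not neutral, because salvage shrinks the difference: at s = 50% the true 20-point gap becomes 92.5% − 82.5% = 10 points.

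**Worked example.** Suppose 48/57 in each arm are controlled by the assigned treatment, leaving 9 failures per arm. PDT stays at 48/57 and some surgical recurrences are credited:

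| Credited of 9 | Surgery | Difference | s0 | z | One-sided p | At 0.025 | At 0.05 |
|---|---|---|---|---|---|---|---|
| 0 | 48/57 | 0 | 0.0723 | 2.77 | 0.003 | passes | passes |
| 4 | 52/57 | −0.070 | 0.0658 | 1.97 | 0.024 | passes | passes |
| 5 | 53/57 | −0.088 | 0.0638 | 1.76 | 0.039 | fails | passes |
| 6 | 54/57 | −0.105 | 0.0616 | 1.54 | 0.062 | fails | fails |

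**The case against.** The strongest reply is that the endpoint is already arm-neutral. Section 12.3 sends both arms to 9.2 and 9.3, and Table 4 scores any new lesion as progression. Response is scheduled for surgery as for PDT (8.7, 8.8, Table 3), so the sentence in 9.3 that names only PDT is a minor slip. The 4.3 sentence sits under salvage surgery and may be no more than a trigger for salvage.

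This stands as far as it goes. The shared criteria fix the score at the visit where a recurrence is seen. They do not say which visit decides the primary endpoint after salvage.

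The second reply is that 7.3 and 7.4 take participants off study at progression, so a re-resected participant may never reach a month-24 examination. That path is indeed uncertain, but leaving does not settle the score. If PDT failures are kept and 25% or 50% of surgical recurrences simply go uncounted, power is nearly the same as with credit: 71% and 53% (200,000 simulations, one-sided 0.025).

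A reader might infer that the plan is biased against PDT, with PDT failures held as failures while surgical recurrences are forgiven. The documents do not establish that. If 4.3 is not linked to the endpoint, it does not fix PDT scoring either, and a salvaged PDT failure could equally read as complete response at month 24. The opposite inference, that the plan is built to credit salvage, is not supported either: 4.3 and section 2 point toward control after initial treatment.

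**Conclusion.** The concern holds in a direction-neutral form: the plan does not determine how progression, recurrence or salvage before month 24 counts in the primary comparison, and its only failure rule covers one arm. This is more than missing detail, since a literal month-24 examination can score a salvaged participant as a complete response.

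The consequence depends on the reading. Leniency to surgery alone costs power and lowers false non-inferiority. Leniency in both arms, or to PDT alone, inflates false non-inferiority, which is the more serious error here. In the example, rescoring five participants reverses the conclusion at one-sided 0.025; at 0.05 it takes six.

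The sizes rest on assumed salvage shares and on the protocol's 85% rate. The gap itself rests on the text alone. Section 8.12 and the study schema were not available for this review and could bear on it.

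**What to change.** Change the analysis definition only; clinical management is untouched. In 9.3 and 12.3, with a cross-reference in 4.3:

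- Define a responder identically in both arms: complete response after the assigned treatment, with no documented residual disease, local recurrence, progression, or salvage treatment for residual or recurrent disease through month 24.
- Count a failure recorded at any study visit, or at the withdrawal evaluation, as non-response in the randomized arm.
- State, the same way for both arms, whether nodal disease or a second primary counts.
- State that best overall response is not the primary endpoint.

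The cost is wording; the assessments are already scheduled in both arms (8.7, 8.8, Tables 2 and 3) and at withdrawal (7.4). There are three downsides. Observed response rates will be lower than under a month-24 snapshot. The salvage component depends partly on the treating physician's judgement in an open-label trial; tying it to documented disease limits this but does not remove it. A partial response at 12–16 weeks that later clears without treatment stays a non-response.

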8.7 ABOUT 12 - 16 WEEKS POST TREATMENT

- Clinical examination with photograph of lesion if possible
- Vital signs (i.e., temperature, heart rate, respiratory rate, blood pressure, and body weight)
- Performance status (ECOG): **Appendix D**
- Response, clinical (for both arms)
- Response, pathological, biopsy for all participants.
- Quality of Life Questionnaire: **Appendix H**

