12.3 EFFICACY ANALYSIS

Objective tumor response will be tabulated overall. All participants who will be randomized to the PDT treatment or surgery will be evaluable for response. Tumor response will be evaluated according to RECIST v1.1. The treating physician will examine the clinical response and a photograph of the treatment site/s will be taken with paper ruler, to determine the reduction in the lesion size. Tumor response will be determined according to the guidelines in sections 9.2 and 9.3.

If clinically indicated, the clinical evaluation will be confirmed with pathological examination of tissue 3-mm punch biopsy that will be taken from the treated region.

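### Read literally, a clear exam with carcinoma on the mandatory 12-16 week biopsy can be scored as complete response, and no rule carries that biopsy into the 24-month primary endpoint

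*Combined protocol and SAP*

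**What the plan says.** **The biopsy.** Section 8.7 lists, at 12-16 weeks, "Response, pathological, biopsy for all participants". Section 9.1 gives its purpose: "Pathological tumor response will be evaluated by taking a 3-mm punch biopsy from the PDT treated or surgical area at 12-16 weeks". Section 4.1.2 says who reads it: "A clinical pathologist will examine the processed tissue section and determine the pathological response". No categories of pathological response are defined.

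**The response rules.** Section 9.2 defines CR as "Disappearance of all target lesions", with a node-size criterion added. Histology enters that section only under partial response and stable disease; for partial response, "A biopsy will be taken from the suspected lesions for histological confirmation of squamous cell carcinoma". Section 9.3 sets the time points: "Time point response assessments will be performed 12 - 16 weeks and 24 months after PDT". Its Table 4 takes target, non-target and new lesions as inputs, and nothing else.

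**The analysis.** Section 12.3 says "Tumor response will be determined according to the guidelines in sections 9.2 and 9.3", and has pathology confirm the clinical evaluation only where clinically indicated. The synopsis (Statistical Analysis) determines response from before-and-after photographs. Sections 3.1 and 12.2 place the primary comparison at 24 months.

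**The failure rule.** Section 4.3 counts progression, local recurrence, partial response and no response as treatment failures, after PDT only. It then adds: "The determination will be performed during the study visits, and based on clinical exam and pathology, if clinical exam is unclear".

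**The concern.** The trial takes tissue from everyone to find out whether carcinoma remains, and then does not connect the answer to the endpoint. If exam and biopsy disagree, no rule says which prevails. The primary test is non-inferiority of a response rate, so a participant with proven residual carcinoma who is counted as a responder makes that arm look better than it is.

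The case need not stay silent for two years to matter. Section 12.1 reports that all earlier non-responders were successfully salvaged by surgery. A PDT participant with a positive biopsy who is then resected could have a clear exam at month 24. The analysis is by randomised arm, and response is judged at that visit under sections 9.2 and 9.3. The clearance produced by surgery could then be credited to PDT.

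**Working it through.** **1. Apply the rules to one participant** with a clear exam at 12-16 weeks and squamous cell carcinoma on the scheduled biopsy.

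- Section 9.2: target lesion gone, so CR. The histology requests under partial response and stable disease are not reached.
- Section 9.3, Table 4: target CR, no other lesions seen, so overall CR. There is no column for histology.
- Section 12.3: a clear exam gives no evident clinical indication for pathological confirmation.
- Section 4.3: the exam is not unclear, so pathology is not called on. If the participant is in the surgery arm, this rule does not apply at all.
- Month 24: section 12.3 returns to sections 9.2 and 9.3. Neither mentions an earlier positive biopsy, the treatment-failure label of section 4.3, or salvage.

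**2. Reproduce the plan's power.** Inputs from section 12.2: 57 per arm, 85% in both arms, margin 0.20, Farrington-Manning test, nominal 0.05. The side of the non-inferiority test is not stated.

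Constrained rates under the null are 0.708 (PDT) and 0.908 (surgery).

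- SE under the null = √[(0.708×0.292 + 0.908×0.092)/57] = 0.0714
- SE under the alternative = √(2×0.85×0.15/57) = 0.0669
- Power at one-sided 0.025 = Φ[(0.20 − 1.960×0.0714)/0.0669] = Φ(0.898) = 81.5%

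Exact binomial enumeration gives 83.2%. One-sided 0.05 gives 89.1% (exact 89.8%). The stated figure of about 80% fits one-sided 0.025 better, so that level is used below.

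**3. Unit of effect.** One misclassified participant moves an arm by 1/57 = 1.75 percentage points.

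**4. Illustration.** Every misclassification rate here is assumed. True rates are put on the null boundary: 65% PDT, 85% surgery. The entry is the exact probability of declaring non-inferiority at one-sided 0.025.

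| Misclassified as response at month 24 | Apparent PDT / surgery | P(non-inferiority) |
|---|---|---|
| None | 65% / 85% | 2.6% |
| 0.5 points, PDT only (5% discordant, one in ten still misclassified) | 65.5% / 85% | 2.95% |
| 2 points, PDT only | 67% / 85% | 4.5% |
| 5 points, PDT only | 70% / 85% | 9.5% |
| 2 points, both arms | 67% / 87% | 2.5% |
| 5 points, both arms | 70% / 90% | 2.5% |
| 2 points, surgery only | 65% / 87% | 1.35% |

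The 5-point PDT-only row requires 5/35, or one in seven, of the true PDT non-responders to be scored as responders.

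**The case against.** **Salvage already implies failure.** Sections 4.1.2, 4.3 and 10.6 describe standard therapy or salvage after PDT as what follows a failure to respond. A surgeon who resects for biopsy-proven carcinoma has in effect applied that category. This is fair as a description of practice, and many clinicians would class the case as failure or local recurrence. It does not close the gap. Local recurrence is undefined, and the primary analysis never turns treatment failure or salvage into non-response at 24 months.

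**Biopsy belongs to the response section.** Section 9.1 opens with it, and nothing tells anyone to disregard a positive result in hand. That also stands: the plan is silent on the conflict and does not direct that carcinoma be ignored.

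**Stronger readings that a reader might infer.**

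- *That the CR rule departs from the Phase I definition, so that the 82% supporting the planning rate was measured differently.* The documents do not support this. The footnote to the Phase I response table in section 1.5.3 says those categories are as defined in section 9.3 of this protocol, and it describes CR in terms of carcinoma having disappeared. If anything, this suggests that residual carcinoma was not meant to be CR.
- *That sites will score such cases differently.* This is inference. Pathology is local (section 8.11) and no central review is described, but randomisation is stratified by site, so a site's scoring habit would tend to fall on both arms.
- *That the error rate is inflated to some stated level.* No discordance rate is given for either arm, and the table shows inflation, no change or a fall depending on what is assumed.

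**Unseen text.** Section 8.12 and the Figure 1 schema were not available to me. A rule in either could answer the point.

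**Conclusion.** The concern holds as a gap in the endpoint definition and should be fixed. The written rules, followed literally, permit CR for a participant with biopsy-proven carcinoma and a clear exam, and they do not carry a positive biopsy or later salvage into the 24-month response. The conclusion rests on the wording of sections 4.3, 9.2, 9.3 and 12.3, and does not depend on the arithmetic.

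The size and direction of any bias are unknown. The illustrative probabilities assume one-sided 0.025, true rates of 65% and 85%, and misclassification that persists to month 24. They show only that the effect matters if it falls mainly on the PDT arm. The sample size and the stated power are not in question here.

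**What to change.** In sections 4.3, 9.2, 9.3 (including Table 4) and 12.3, state for both arms:

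- Squamous cell carcinoma on any post-treatment protocol biopsy of the treated area is not CR and counts as non-response in the 24-month primary analysis, whatever the clinical exam shows and whatever salvage follows.
- This covers the 12-16 week biopsy, any later biopsy, and a 4-6 week biopsy of a suspicious lesion that leads to salvage.
- The section 4.3 condition about an unclear exam is deleted for biopsies already taken.
- Dysplasia without carcinoma may remain CR, as in the Phase I response table.

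As a minor consistency edit, align the footnotes to Tables 2 and 3, which list a response biopsy at 2 years, with sections 4.1.2 and 8.8, which take one only if clinically indicated. No new mandatory procedure is needed.

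**Cost.** Wording only; the 12-16 week biopsies are already scheduled in both arms. Observed response rates, and so power, may be slightly lower. As illustration, exact power at one-sided 0.025 is 83.2% at 85%/85%, 79.9% if both arms fall to 83%, and 73.0% if PDT alone falls to 83%.
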